Sample size determination. We will enroll 66 participants and expect 50 to complete the study. This drop-out rate accounts for participant non-compliance. In our previous Sleep Study, our completion rate was 90%. We expect a larger drop-out rate in the proposed study due to the longer duration of each treatment phase, and we also anticipate dismissing some participants due to non-compliance. Each participant will undergo 2 study phases, and each response variable will be measured at least once per phase. Thus, for each response measure we will have at least  $50 \times 2$  paired observations. We have analyzed preliminary data consisting of a number of measurements from 2 overweight women from our Pilot Study. Based on preliminary data analysis we have estimated an effect size (mean paired difference) of  $0.69 \pm 0.36$  g for fat mass and an effect size (mean paired difference) of  $0.91 \pm 0.65$  g for weight gain. This translates to very large effect sizes of 1.92 (fat mass) and 1.4 (weight gain) for paired t-tests. With these effect sizes we have more than 99% power for paired t-tests.] We have estimated the EI effect size to be  $295.9 \pm 116.3$  kcal [8]. The effect size for a paired t-test (effect size divided by the standard deviation) for a paired t-test is >2, which is a very large effect size for paired t-test. This means with  $50 \times 2$  paired samples, we have >80% power for paired t-test. In [name] et al. 2011 [8], we also reported an effect size of  $20.7 \pm 6.8$  g for fat intake and an effect size of  $57.9 \pm 32.6$  g for carbohydrate intake. This translates to very large effect sizes of 3.04 and 1.78, respectively for fat and carbohydrates for paired t-test. With these effect sizes we have >80% power for paired t-test. Moreover, using the R^2 value from our linear model analysis of [name] et al. 2011, we determined that we have >80% power for proposed linear mixed model analyses (as described in statistical plan) with energy balance, fat and carbohydrate intakes. Thus, we have very good power overall, which will be useful in our primary analyses as well as in exploring sex differences. Statistical plan. Exploratory data analyses for physiological, anatomical, biomarker and intakerelated responses will be performed using R, SAS and other software. As part of the analysis, we will compute descriptive statistics for each variable. In particular, we will compute the proportion, mean, variance, standard error and the range of continuous variables and frequency and mode for discrete variables. Descriptive statistics will be computed for each specific sleep phase. In addition, correlation coefficients between the variables will be computed and scatter plots will be checked for linear relationships. The correlations and scatter plots help assess the degree of collinearity among variables, which will be useful for interpreting regression-based linear mixed model analyses discussed later. The data will be tested for normality, and if needed an appropriate transformation will be used on the raw data to make the normal approximation better. We will have a comprehensive strategy to deal with missing data. We will study missingness to decide if the data are missing at random or missing completely at random. Missing rates will also be estimated for each variable. Missing values will be imputed, as appropriate. We will fit a linear mixed model to analyze the data. Treatments (sleep duration: SR vs. HS) will be fixed effects and subjects a random effect. As we are collecting data from two phases for each subject, we will test for carryover effects by using a treatment x phase interaction in an initial version of each linear model. If the interaction term is not significant then we will rebuild the linear model without the interaction term. The other independent variables (covariates) will be sex, age, baseline BMI, and race/ethnicity. If required anywhere in the analysis plan, p-values will be adjusted for multiple comparisons. Sp. Aim 1: Hypothesis 1a. SR will lead to increased total adipose tissue mass, as assessed using MRI, relative to HS. We will perform repeated measure linear mixed model analyses separately for adipose tissue mass increase and weight gain (as the response). Sleep duration (SR vs. HS) and the covariates will be used as independent variables. Subject will be used as a random effect. Paired t-test and Wilcoxon test will be used to determine whether the SR and HS have different

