
effects on weight gain and adipose tissue mass increase. Hypothesis 1b. EE, assessed by DLW, and physical activity level, monitored daily by actigraphy, will be lower during SR relative to HS. We will perform repeated measure linear mixed model analyses separately for DLW and actigraphy-derived variables as the responses. Sleep duration (SR vs. HS) and the covariates will be used as independent variables. Subject will be used as a random effect. Paired t-test and Wilcoxon test will be used to determine whether SR and HS have different effects on DLW and actigraphy measures. Sp. Aim 2: Hypothesis 2a. EI, assessed by [3-d food records], will be greater during a period of SR relative to HS. This will be mostly due to increased fat and carbohydrate intakes. We will perform a repeated measure linear mixed model analyses separately with each EI measure (as the response) and sleep duration (SR vs. HS) and the covariates as independent variables. Subject will be used as a random effect. Paired t-test and Wilcoxon test will be used to determine whether the SR and HS have different effects on EI measures. Hypothesis 2b. Neural responses to food stimuli, assessed by fMRI after 6 wk of SR or HS, will indicate increased activity in networks associated with reward and food valuation (insula, orbitofrontal cortex) during a period of SR relative to HS. These responses will be correlated with intakes of high carbohydrate and high fat foods (hypothesis 1a) and [ghrelin]. Connectivity of the networks involved in reward valuation at rest will be stronger after SR compared to HS and synchrony of the DMN will be reduced after SR compared to HS. Sp. Aim 3: Hypothesis 3a. SR will lead to [increased glucose, insulin, triglycerides, and reduced highdensity lipoprotein cholesterol and adiponectin relative to HS.] We will perform repeated measure linear mixed model analyses separately for each of glucose, insulin, triglycerides, high-density lipoprotein cholesterol and adiponectin. Sleep duration (SR vs. HS) and the covariates will be used as independent variables. Subject will be used as a random effect. One-sided paired t-test and Wilcoxon test will also be used to determine whether the SR and HS have different effects on the cardio-metabolic risk profiles, as well as the direction of the effects. Hypothesis 3b. Increased adiposity and poor diet quality (higher fat and carbohydrates) after SR will partially explain the adverse cardio-metabolic risk profile associated with SR. We will select the cardiometabolic risk profile variables that are adversely associated with SR. Then, we will compute the difference in those variables in SR vs. HS (i.e. the value of each variable in SR minus the value of that variable in HS). Using a linear model analysis, we will test if these differences are associated with increased adiposity and poor diet quality. If, for some variables, there are multiple observed differences for each subject then a linear mixed model analysis will be used with subject as a grouping variable. A separate analysis will be performed for each such difference, with the difference as the response variables and adiposity, food quality variables and the covariates as dependent variables. *Linear Mixed Model Analyses.* We will fit a linear mixed model to analyze the data. Treatments (SR vs. HS) will be used as fixed effects and subject will be used a random effect. The other independent variables, such as demographic variables, will be covariates. Those covariates will be removed if they do not significantly contribute to the model. Aim 4: (To determine whether long-term mild SR, relative to HS, challenged acute cognitive outcomes in older and younger adults. Hypothesis 4a. Mild SR will induce cognitive decline, assessed using with the NIH Toolbox, which will be greater in older relative to younger adults.) Outcomes are measures from the NIH Toolbox. Each outcome will be analyzed in separate linear mixed model analyses, for older and young participants, as detailed in "*Linear Mixed Model Analyses*" section above. Sleep (SR vs. HS), along with phase (1 vs. 2), carryover effects, and covariates (if they are found to be significant in an initial analysis) will be used in the model. Subject will be used as a random effect. Then, we will pool the datasets to include both older and young participants. In the pooled dataset, we will use the average differences in NIH Toolbox measures (from HS to SR) as outcomes in linear model analysis. Age group (older vs. younger) will be used as main predictor variable. We will also apply covariates as independent variables, if they are found to be significant in an initial analysis. We will use unpaired t-test on the average difference in

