**Subject Population Justification:**

Two hundred fifty men and pre-menopausal women, age 20-40 y and 55-75 y, BMI 25-35 kg/m^2, or with BMI 20-24.9 kg/m^2 who have at least one parent who has ever had a BMI >27 kg/m^2, will be recruited from the New York City area (target accrual: n=79). These individuals are considered at risk of obesity, making this study group relevant for obesity prevention efforts. Participants who will be recruited to participate in this study will habitually sleep 7-9 h/night, will be free of any current and past sleep and psychiatric disorders, including eating disorders (ex. anorexia, bulimia, night eating syndrome), and will not have diabetes or CVD, and have normal scores on all screening questionnaires. Participants with resistant hypertension will be excluded.

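### Age stays eligible as a covariate beside age group in the pooled Aim 4 and Aim 5 models, and under one reading of an undefined screen the age-group coefficient loses most of its power

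*Combined protocol and SAP*

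**What the plan says.** All of the following is in Statistical Procedures unless stated.

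- The statistical plan names the covariates: "The other independent variables (covariates) will be sex, age, baseline BMI, and race/ethnicity".
- The paragraph on linear mixed models gives a general rule: "Those covariates will be removed if they do not significantly contribute to the model".
- For Aim 4, after separate models in older and younger participants, the data are pooled and "we will use the average differences in NIH Toolbox measures (from HS to SR) as outcomes in linear model analysis". Then: "Age group (older vs. younger) will be used as main predictor variable". Covariates are added under this rule: "We will also apply covariates as independent variables, if they are found to be significant in an initial analysis".
- The next sentence plans a second, unadjusted test of the same contrast: "We will use unpaired t-test on the average difference in" the Toolbox measures between the two groups.
- Hypothesis 4a is that the decline under sleep restriction exists, "which will be greater in older relative to younger adults".
- The pooled Aim 5 model also contains age group and uses the same covariate rule. It has no unadjusted companion test.
- Subject Population Justification gives the bands: "Two hundred fifty men and pre-menopausal women, age 20-40 y and 55-75 y".

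The plan does not say what the initial analysis is, whether it holds age group, or what significance level applies. Its look at collinearity is meant to help interpretation and excludes nothing.

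**The concern.** In the pooled model age group is a coarse version of age. A person's age in years fixes the group exactly, and no one is aged between 40 and 55. With both terms in the model, the age-group coefficient is no longer the older v younger difference. It is the part of that difference left over after a straight line in age, carried across the empty gap.

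A larger effect in older people also tends to make age significant when it is screened without age group. The rule can therefore bring age in most often when Hypothesis 4a is true. At stake is the only model-based test of that hypothesis: a real difference could appear as a wide, non-significant coefficient, sometimes with the wrong sign, beside a significant t-test.

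**Working it through.** **No plan figure to reproduce.** The documents give no effect size, SD, group size, alpha or power for the pooled contrast.

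**Inputs from the documents.** Bands 20-40 and 55-75 y; 66 younger participants planned; target accrual 79; 45 accrued and 36 completed (Subjects).

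**Assumptions.** Ages uniform within band; 79 - 66 = 13 older at target (an inference); 9 older among 36 completers; SD 1 for the within-person difference; true group difference 1 SD; two-sided 0.05; 'age' read as age in years.

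**Collinearity.** Band means are 30 and 65, a difference of 35. Within-band variance is 20²/12 = 33.3. With p the older fraction, R² = p(1-p)·35² / [p(1-p)·35² + 33.3], and VIF = 1/(1-R²).

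- 13 of 79: 0.1375 × 1225 = 168.4; R² = 168.4/201.7 = 0.835; VIF 6.05; SE × √6.05 = 2.46.
- 9 of 36: 0.1875 × 1225 = 229.7; R² = 229.7/263.0 = 0.873; VIF 7.89; SE × 2.81.

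Other splits (50/13, 26/10, 25/25) give VIF of 7.0 to 10.2.

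**Direct check, step effect of 1 SD.** Power ≈ Φ(1/SE - t critical).

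- 79 people, group only: SE = √(1/66 + 1/13) = 0.303; Φ(3.30 - 1.99) = 0.90. With age: SE = 0.303 × 2.46 = 0.746; Φ(1.34 - 1.99) = 0.26.
- 36 people, group only: SE = √(1/27 + 1/9) = 0.385; Φ(2.60 - 2.03) = 0.72. With age: SE = 0.385 × 2.81 = 1.08; Φ(0.92 - 2.03) = 0.13. The coefficient has the wrong sign with probability Φ(-0.92) = 0.18.

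**Power of the age-group coefficient under the whole procedure (simulation).**

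| People (older) | True effect | Group only | Age screened without age group | Age screened beside age group |
|---|---|---|---|---|
| 79 (13) | step | 90% | 29% | 88% |
| 36 (9) | step | 72% | 19% | 71% |
| 79 (13) | linear in years | 90% | near 5% | 64% |
| 36 (9) | linear in years | 69% | near 5% | 59% |

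Screened without age group, age enters in 83% (79) or 65% (36) of trials for a step effect. Screened beside age group, it enters in about 5%.

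**Estimate.** With a step effect and age in the model, the mean coefficient is 1.00 (79) and 1.03 (36): unbiased, only less precise. If the effect is linear in years, the true coefficient given age is zero, so the test rejects at about its nominal rate. At 50/13, 26/10 and 25/25, with the difference set for 80% unadjusted power, the screened procedure had 5-6% power.

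**No true difference.** At those three splits, screening age beside age group gave a false-positive rate of about 8% for the age-group term; screening without it gave about 2%.

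**Remedy.** Centring age within group makes it uncorrelated with age group. Power is then 90% (79) and 71% (36) for the step effect.

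**The case against.** The strongest answer is that the plan already tests the same contrast without covariates. The unpaired t-test has the group-only power under every reading. A reader might infer that Hypothesis 4a has no sound test left; the documents do not support that. What remains is that the plan does not say which result decides if the two disagree, and Aim 5 has no such second test.

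Second, a reader might infer that age is bound to pass the screen when the hypothesis is true. That needs the initial analysis to omit age group, which the text does not say. The nearest wording, on removing non-significant terms from a fitted model, suggests elimination with the main predictor already present, though it is written for the mixed models. On that reading a step effect is almost unharmed. A linear one still loses power, and the false-positive rate rises somewhat.

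Third, a reader might say that age absorbs the contrast. That is true only for an effect linear in years. For a step effect the loss is in precision, and a reversed sign is sampling error.

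Fourth, 79 is a target that was not reached: enrolment is closed with 45 accrued and 36 completers. The 36-person figures are nearer to what exists, but the 9 older among them is assumed.

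**Conclusion.** The defect stands in a conditional form. Age is an eligible covariate beside age group in two pooled models, nothing removes it, and the two are nearly collinear by design. How much this costs depends on a screen that the plan leaves undefined and on the shape of the true effect. The age-group coefficient's power may be almost untouched, fall from 90% to 64%, fall to 29% or 19%, or vanish.

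The collinearity rests on the stated bands plus assumed group sizes and uniform ages. The power figures also rest on the assumed 1 SD difference and 0.05 level. For Aim 5 the same wording creates the same overlap, but no power loss was computed. The point is worth settling because the remedy is specific and nearly free, not because Aim 4 lacks a usable test.

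**What to change.** State that age in years is not a covariate in the pooled Aim 4 and Aim 5 models, or that it enters only as the deviation from the mean age of the person's own group. Keep age in the models fitted within each age group. State that the age-group contrast without age decides Hypothesis 4a; with no other covariates this is the same comparison as the planned t-test with equal variances.

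The cost is a few sentences and a re-run of the pooled models, with no new data. Renewal Information describes the study as open only for analysis and reporting, with a cognitive paper in press. So the change should be labelled post hoc wherever results have already been seen, and the report should say which covariates the pooled models contained.

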
NIH Toolbox measures (from HS to SR), to test if these values are significantly different between older and young participants. Aim 5: (To determine whether the effects of SR on cognitive outcomes are moderated by brain atrophy in younger and older adults. Hypothesis 5a. The effect of mild SR on cognition will be greater among individuals with greater amounts of cortical thinning, smaller hippocampi, and greater WMH volume. This effect will be greater in older relative to younger adults.) Separately for older and young participants, we will perform linear model analyses, with average differences in NIH Toolbox measures (from HS to SR) as outcomes (separately for each outcome). Cortical length, hippocampi size and WMH volume will be used as independent variables. We will apply covariates as independent variables, if they are found to be significant in an initial analysis. Then, we will pool the datasets to include both older and young participants. In the pooled data, we will perform linear model analyses, with average differences in NIH Toolbox measures (from HS to SR) as outcomes. Cortical length, hippocampi size, WMH volume and age group (older vs. younger) will be used as independent variables. We will also use covariates as independent variables, if they are found to be significant in an initial analysis. Aim 6: (To determine whether changes in metabolic or hormonal profiles mediate changes in cognitive function as a result of SR. Hypothesis 6a. The effect of mild SR on cognition will be mediated by changes in hormones (leptin, adiponectin, and insulin).) Separately for older and young participants, and separately for each hormone measure, each outcome (from NIH toolbox) will be analyzed with mediation analysis (Baron and Kenny's method). Sleep type (SR. vs HS) will be the predictor in the analysis. Hormone measure will be used as the potential mediator. As we have multiple measures from each participant, each component analysis in Baron and Kenny's method will be done as linear mixed model analysis, with subject as random effect. Within each mediation analysis, the first analysis will only have one fixed effect: sleep (SR vs. HS). The outcome measure will be the dependent variable. If sleep is found to be significant, then the second analysis will be done with the hormone measure as the dependent variable, and sleep as the fixed effect. If sleep is also found to be significant in the second analysis, then in the final analysis, the outcome measure will be the dependent variable. Fixed effects will be sleep and the hormone measure. If the hormone measure is still found to be significant, and the coefficient of sleep has decreased in absolute value from the first analysis, then a mediation effect of hormone will be concluded.

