Structural brain imaging MRI protocol. MRI scanning will take place on a 3T Philips Achieva scanner located at Columbia University Irving Medical Center. This procedure will take place in conjunction with the whole-body scan that is currently performed in the parent study and will only be performed at baseline of phase 1. The protocol derives measures of brain atrophy/volumetry and WMH, but we will also examine microbleeds and infarcts for secondary analyses. Table 1 displays the pulse sequences collected for this study. Scanning takes place in a single session and includes a high-resolution T1-weighted anatomical scan (MPRAGE), T2-weighted FLAIR, and gradient echo (GRE). We also collect diffusion-weighted imaging and diffusion tensor imaging data for secondary or exploratory analyses. The MRI data will be transferred to a PACS for clinical review and via established, secure DICOM servers the data are also transferred to [name] laboratory for analysis.

Global and regional atrophy. Using each individual's T1-weighted image, structural imaging measures of both global and regional brain volume and measures of cortical thickness are derived with FreeSurfer (<http://surfer.nmr.mgh.harvard.edu/>). Primary volumetric measures will be hippocampal, entorhinal cortex, and total brain volume. We will also assess cortical thickness as specific patterns of cortical thinning found in Alzheimer's disease [20, 46]. Again using Freesurfer software [47, 48], we will calculate mean thickness in 33 different gyral-based areas in each hemisphere [49]. The primary cortical thickness measure [20, 46] will include the average thickness in Alzheimer's disease -related regions [50]. Volumetric and cortical thickness in all regions are databased for secondary analyses.

Microbleeds. Microbleeds are rated by visual inspection following criteria put forth by Greenberg et al. [51-53]. The primary measure is the presence or absence of lobar microbleeds, indicating possible or probable cerebral amyloid angiopathy [54]. The number of microbleeds and location are coded and databased for each participant.

Infarct. All available MRI data are used to define radiological infarcts. Infarcts are rated as discrete hypointense lesions that are larger than 5mm surrounded by a complete hyperintense ring on FLAIR. The primary measure is presence or absence of infarct, but several summary measures are generated, including number, size, and location.

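### Aim 5 specifies no head-size adjustment for hippocampal or WMH volume and keeps age in years and sex only if significant, which leaves head-size variation and within-age-band confounding in the moderator test

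*Combined protocol and SAP*

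**What the plan says.** Under Statistical Procedures, Hypothesis 5a expects a larger cognitive effect of sleep restriction in people with "greater amounts of cortical thinning, smaller hippocampi, and greater WMH volume", and expects this to be stronger in older adults. The outcome is each person's average HS-to-SR difference on the NIH Toolbox measures.

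- **Stratified models.** "Separately for older and young participants, we will perform linear model analyses". In these, "Cortical length, hippocampi size and WMH volume will be used as independent variables".
- **Pooled model.** "Cortical length, hippocampi size, WMH volume and age group (older vs. younger) will be used as independent variables". Age group enters without a significance test.
- **Covariates.** The list is given earlier in the same section: "The other independent variables (covariates) will be sex, age, baseline BMI, and race/ethnicity". For Aim 5, "We will apply covariates as independent variables, if they are found to be significant in an initial analysis". The general mixed-model paragraph has a matching rule: "Those covariates will be removed if they do not significantly contribute to the model".
- **Imaging.** The structural brain imaging text in Procedures schedules one scan, at baseline of phase 1, processed with FreeSurfer. "Primary volumetric measures will be hippocampal, entorhinal cortex, and total brain volume".

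Intracranial volume, head size and normalisation are not mentioned anywhere. Total brain volume is derived but is not in the Aim 5 model. No power, sample size or effect size is given for Aim 5.

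**The concern.** With one scan per person, atrophy has to be read from a cross-sectional volume, and a small hippocampus may simply belong to a small head. Head size also differs between the sexes, and the accrued sample is 49% female, yet sex stays in the model only if it reaches significance. If head size has nothing to do with the sleep effect, it is noise in the moderator and weakens the test.

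Age in years can plausibly relate to both brain structure and the sleep effect within 20-40 y and within 55-75 y. In groups this small a significance screen often drops a covariate that matters, and the brain term then picks up part of the age effect. A null result could therefore reflect head-size noise, and a positive one could reflect age within the band.

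**Working it through.** **The plan's own figure.** There is none for Aim 5. The only power statement close to it is for Aim 1 (above 99% for fat mass and weight gain). It reproduces: 0.69/0.36 = 1.92 and 0.91/0.65 = 1.40, with power above 0.99 at n=50. It says nothing about a moderator regression.

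**Inputs from the documents.** 66 enrolled and 50 expected completers in the parent cohort (Sample size determination); target accrual 79 and 36 completers, younger and older together (Subjects). About 13 older adults is an inference: 79 - 66 = 13. The younger Aim 5 sample may be smaller than the parent cohort, because only participants enrolled during the supplement award receive the added tests.

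**Assumed inputs.** Two-sided alpha 0.05; head size explains a share s = 0.20 to 0.50 of volume variance; the true correlation of atrophy with the outcome is 0.4; head size is unrelated to the outcome. The documents give none of these.

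**Head size, by hand.** Write volume = sqrt(1-s) x atrophy + sqrt(s) x head size. The correlation the model sees is 0.4 x sqrt(1-s), and power is about Phi[atanh(r) x sqrt(n-3) - 1.96]. At n=36, sqrt(33) = 5.745:

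| s | r seen | atanh(r) x 5.745 | power |
|---|---|---|---|
| 0 (head size removed) | 0.400 | 2.43 | 68% |
| 0.20 | 0.358 | 2.15 | 58% |
| 0.35 | 0.322 | 1.92 | 48% |
| 0.50 | 0.283 | 1.67 | 39% |

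The unadjusted slope is 1-s of the adjusted one. For head-size correlations of 0.3, 0.5 and 0.7 (s = 0.09, 0.25, 0.49) the ratio is 0.91, 0.75 and 0.51. If sex happens to be retained (assumed sex-head size correlation 0.6), it recovers part: 0.94, 0.82 and 0.62.

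**Head size, simulated with all three imaging predictors in the model.** At n=36, power is about 36-54% without a head-size term. It is 61-66% with one; the lower end (61-63%) applies when age and sex are also in. At n=13 and s = 0.20/0.35/0.50, power is 19/16/14% as planned and 16/18/17% with intracranial volume, age and sex all added, which is no useful gain.

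**Age within a band.** With no true moderation, omitting age leaves a spurious brain-outcome correlation equal to the product of the two age correlations: 0.2 x 0.2 = 0.04, 0.3 x 0.3 = 0.09, 0.6 x 0.4 = 0.24. Simulated type I error for the brain term in a stratified model:

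| Rule for age | Age correlations 0.2-0.3 | Age-brain 0.4-0.6, age-outcome 0.3-0.4, n=25-50 |
|---|---|---|
| Screened in the joint model | about 5-8% | about 8-18% |
| Screened alone against the outcome | about 5-7% | about 5-7% |
| Always in | about 5% | about 5% |

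The plan does not say which screen its initial analysis is. The screen is weak at small n: with 13 people and age correlations of 0.2-0.5, it kept a truly relevant age term in only 8-19% of runs.

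**Age in the pooled model** (age-brain 0.3-0.7, age-outcome 0.3-0.5): type I error is 9.0-30.5% with no age term, 5.0-7.8% with age group plus the screen as planned, and 4.6-5.3% with age in years also forced in. The age-group term does most of the work.

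**Degrees of freedom at n=13.** Three imaging terms plus intercept leave 13 - 4 = 9. Adding intracranial volume, age and sex leaves 13 - 7 = 6. Normalised volumes plus age and sex leave 13 - 6 = 7.

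**The case against.** Several stronger readings are tempting, and the documents do not support them.

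- **That raw volumes are entered.** The text is silent. FreeSurfer derivation is described without saying whether volumes are normalised, and the supplement protocol is listed as an attachment that is not part of these documents. The defect is that adjustment is not specified.
- **That Aim 5 is confounded by age outright.** The separate models and the always-present age-group term remove the difference between the 20-40 y and 55-75 y groups. Only confounding within each 20-year band remains.
- **That type I error approaches 20%.** That needs age-brain correlations near 0.6 inside a 20-year band and a joint-model screen. No figure in the documents supports such values.
- **That the effect is always dilution.** This holds only if head size is unrelated to the sleep effect. Otherwise the bias can go either way, which is also a reason to adjust.
- **That the fix is free.** In an older group of about 13 it costs scarce degrees of freedom and brings almost no power, although this is where atrophy and WMH are expected to matter most.

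It is also fair to say that n=36 and n=50 are not the Aim 5 stratum sizes, and that cortical thickness lies outside the head-size argument. What stands is the missing head-size specification and the significance screen on age in years and sex.

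**Conclusion.** The concern holds as a gap in specification with a moderate, uncertain effect. At n=36 the assumed range implies a loss of roughly 10 to 25 points of power from unadjusted head size, and almost none that can be recovered at about 13. The age screen inflates type I error slightly under modest within-band correlations and materially only under strong ones with a joint-model screen. Every correlation, the alpha and the older-group size are assumptions or inferences. The direction is secure provided head size is unrelated to the outcome; the magnitude is not. The change is worth making because it costs little, and because the plan leaves open how its screen is applied.

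**What to change.** 1. State one head-size method for hippocampal and WMH volume in advance, using intracranial volume estimated from the existing T1 scan: either normalised volumes or intracranial volume as a covariate. These are different models, so choose one. Normalised volumes save a degree of freedom in the small older group.
2. Keep age in years and sex in every Aim 5 model, stratified and pooled, whatever their p-values.
3. Reconcile the cortical predictor: the Aim 5 models name a length, while the hypothesis and the imaging section refer to thinning and thickness.
4. Enrolment is closed, the study is open only for analysis and reporting, and a paper on cognitive function is in press. If any Aim 5 result is already known, report the revised models as a labelled sensitivity analysis beside the planned ones.

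The cost is one derived variable and a few sentences of SAP text, with no new scans, visits or participants. The downside is two or three degrees of freedom, which matters mainly in the older stratum. That model should be reported with its residual degrees of freedom and confidence intervals, and read as imprecise.
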